##### 1.2 Study Procedures, Materials, and Potential Risks:

###### Study Procedures:

Participants will be screened over the phone to determine initial eligibility. Alternatively, participants may complete a redcap survey to determine initial eligibility. Participants will see a script that briefly explains the study. Once participants have been determined to be initially eligible, they will be invited to participate in the consent process. The consent process will take place via one of the following modalities: 1) Remote electronic

[figure not shown]

Figure 3a: Hypothetical Changes in CPD over sampling

[figure not shown]

Figure 3b: Impact on reduction in CPD

consent (e-consent) via REDCap facilitated with a discussion over the phone, 2) Remote consent via doxy.me, or 3) in-person consent (in-person visit at start of Visit 1). During the COVID-19 restrictions, all consenting will be done remotely (not in-person). We have built in the option for electronic consent to reduce the length of the first in-person visit and while still providing ample time for the consent process. Consented participants will be asked to attend an in-person screening session. Participants will be asked to provide a carbon monoxide sample to confirm smoking status, and women will provide a urine sample for pregnancy testing. Participants will then complete a series of interview-administered and participant-administered questionnaires that assess brief medical history, tobacco use history including prior and current e-cigarette and cigarette use, current use of smoking cessation products, and demographics. After all questionnaires have been completed, study staff will determine participant eligibility.

Participants who are eligible will then provide a urine sample for cotinine analysis and complete additional baseline questionnaires including measures of nicotine dependence. Participants will be randomized to one of four groups as described above and will have the opportunity to sample their usual brand cigarette and their assigned e-cigarette and e-liquid for the first time. After sampling each product, participants will complete additional questionnaires and complete the preference assessment where they choose between their cigarette and assigned e-cigarette. At the end of Visit 1, participants will receive a one week supply of e-liquid to take home with their assigned e-cigarette, will be enrolled in the daily electronic diary system, and will be provided with instructions for completing diaries.

Participants will return to the lab for three additional weekly visits, and will receive a new supply of e-liquid for each week. At each visit, we will assess tobacco use during the prior week, participants will provide an expired breath carbon monoxide sample, adverse events will be assessed, and participants will complete questionnaires about their assigned e-cigarette and e-liquid. At the fourth and final weekly visit, participants will complete the sampling and preference assessment again, providing another urine sample for cotinine testing, and return any unused study product.

### **Materials:**

Research material obtained from the participants include responses to questionnaires collected directly by our research team and entered directly within secure databases. Data will be stored in a password protected redcap database and on password protected network storage. Consent forms will be stored in a separate locked filing cabinet or electronically on Redcap or a secure Box account. Physiological measures include: urine collected for pregnancy testing, as well as expired breath carbon monoxide. Research data will be obtained specifically for research purposes. Every effort will be made to maintain subject confidentiality, in accordance with HIPAA. For participants recruited from the MUSC EHR, the recruitment project will also be housed in REDCap and only CITI and IRB certified personnel will have access to the database. The research team will only have access to the REDCap recruitment project while actively enrolling participants for the study. The recruitment project will be stored separately from the other study REDCap projects.

### **Potential Risks:**

The research protocol calls for smokers to use e-cigarettes in the lab and (if they desire) at home. E-cigarettes are no more harmful than conventional cigarettes, and various studies suggest that they may offer reduced harm. Questionnaires and interviews are all non-invasive and involve minimal risk to study participants.

Potential risks are as follows:

#### ***E-Cigarettes***

E-Cigarettes are not combusted, and therefore levels of carcinogens are markedly reduced, if not eliminated, comparable to trace levels seen in nicotine replacement products . E-liquid will contain propylene glycol, which some suggest may be harmful. Propylene glycol is an FDA approved food additive, but with uncertain effects upon inhalation.

As for adverse events, the majority of e-cigarette studies are based within on-line surveys. We report here on three moderate to large such surveys. In the first , three side effects were reported by >20% of respondents: headaches (21%), cough (27%), and increased phlegm (25%). In the second , the most common negative effect of e-cigarette use was throat and mouth irritation, and fewer than 3% “reported a high level of side effects.” Finally, the largest online survey to date  did not fully assess adverse events, but reported that 26% of e-cigarette users reported burning in throat. In a cross-over study of 40 smokers given e-cigarette for four days , the four most common adverse events (within highest dosage group) were

mouth/throat irritation (38%), nausea (29%), vertigo (21%) and headache (22%). All other adverse events were rare (<5%).

In the recent RCT from New Zealand , there was a higher number and proportion of adverse events among active e-cigarette group, but the event rate did not significantly differ as compared to nicotine patches. In the RCT from Italy  there was no differential rate of adverse events among high, medium, or placebo e-cigarette groups. The five most common adverse events were dry cough, mouth irritation, shortness of breath, throat irritation, and headache, with no serious adverse events. The study also reported no significant changes in body weight, resting heart rate, or blood pressure.

[figure not shown]
There have been a small number of reports to the FDA of people using e-cigarettes and experiencing seizures, with most reports involving youth or young adult users. This is rare and will be monitored. We have added an exclusionary criteria for history of seizure disorder.

There have been a number of reports of respiratory illness, and even some deaths from that respiratory illness, among individuals using e-devices. No specific substance or product has been linked to these cases. Many of but not all of the cases involved users vaping THC, the active ingredient in marijuana. Some of the instances are specific to nicotine alone. We advise all participants not to add any substances to the devices we give them. We advise against using any e-device or e-liquid that is obtained by questionable or unknown sources (such as off the street or on the black market). While we believe that e-cigarettes are less harmful for adult smokers than regular cigarettes on a long-term basis, there may still be short term risks of using e-cigarettes. We will continue to monitor your health in our study by asking you at every study contact a set of specific questions about any changes you have experienced since the last study contact.

### **Concurrent use of e-cigarettes and smoking**

If smokers engage in dual use, the major concern will be too much nicotine intake. Symptoms of nicotine intoxication include nausea, dizziness, headache, and stomachache . In [name] two prior studies, wherein participants who used nicotine gum/lozenge and smoked concurrently, there was no evidence of nicotine intoxication , nor have we seen serious adverse events in our current e-cigarette studies. We recently completed a literature review  that showed combined NRT, as well as concurrent use of NRT and smoking, were both safe.

A recently completed short-term observational study included 20 smokers who were provided e-cigarettes for ad libitum use over a 2-week period. Data below demonstrate that changes (increases) in e-cigarette use increased in direct proportion with changes (decreases) in cigarette smoked (1st and 2nd panel), resulting in no net change in nicotine (3rd panel). Thus, smokers who engage in dual use are likely to NOT increase total nicotine intake, a finding replicated elsewhere . These findings are very much consistent with [name] prior work on smokeless tobacco, wherein smokers were provided with snus to use ad libitum over two weeks, finding no net increase in nicotine intake.

### **Undermining Cessation**

Another potential risk is that the sampling intervention will decrease rather than increase future cessation. We are aware of one recent longitudinal study  that showed numerically lower but still statistically similar rates of non-smoking among e-cigarette users vs. non-users, but this study did not assess for timing of e-cigarette use. This is the only study to show this that we are aware of. However, most of the available data available suggest that e-cigarettes either do not affect cessation or increase it .

### **Use of E-cigarettes among non-participants and non-smokers, including children**

Whenever a product is given to a smoker to take home and use, there is potential that the product will be used by someone else, inclusive of non-smokers and even children. In [name] recently completed snus trial in which he mailed tins of smokeless tobacco to smokers all over the country, such "diversion" was not a problem. We will advise participants who receive e-cigarettes to keep them out of reach of children and pets.

### **Confidentiality**

A final risk is breach of confidentiality.

## **2. Adequacy of Protection Against Risks**

### **2.1 Informed Consent:**

All research personnel have up to date CITI Certification for Protection of Human Subjects, and will keep this training current throughout the course of the study. Study participants will be recruited through local media outlets (e.g., craigslist, flyers, print ads, facebook). Those who call expressing interest in study participation will be screened for an initial eligibility determination. We will also submit a Research Data Request to obtain a recruitment report of MUSC patients who potentially meet eligibility criteria. The study team will not cold-contact any patients who have opted out of receiving contact about research or who have met the maximum number of contact attempts at the time of recruitment. We will reach out to these potential participants via MyChart message, text message, phone call, or email no more than three times via any one contact method. Once initial eligibility has been determined, the consent process will be initiated. The consent process will take place via one of the following modalities: 1) Remote electronic consent (e-consent) via REDCap facilitated with a discussion over the phone, 2) Remote consent via doxy.me, or 3) in-person consent (in-person visit at start of Visit 1). We have built in the option for electronic consent to reduce the length of the first in-person visit and while still providing ample time for the consent process. All participants will be provided with a hard copy and/or electronic copy of the consent form. Participants will be given time to review the consent documents, as well as a detailed overview of the consent documents by study staff. After participants have read the documents and the documents have been described by the study staff, participants will demonstrate that they understand key aspects of the study by verbally answering questions from study staff about participation (e.g., "Can you tell me what the risks of participation are?"). Participants will sign the consent form only after both the participant and the study staff member are confident that the participant understands their participation and the risks associated with participating. Consent signatures may be collected on paper or electronically. When consent is collected electronically, our study team has a combination laptop/tablet that will be used for the eProcess. No information will be stored locally on the laptop/tablet; all information will be stored securely in REDCap/Box folder if captured electronically. The HIPAA form can be signed on paper or electronically. For the electronic process, all pages of the approved HIPAA document will be uploaded into REDCap for review by the participant. Instead of signing on paper, a participant will enter his/her name, date, and sign electronically (with mouse or finger) in REDCap. Each participant will still receive a paper copy of the "Notice of Privacy Practices" and each signed HIPAA can be downloaded from REDCap as a PDF. These procedures will be done on our research team's combination laptop/tablet, but no data will be stored on the laptop/tablet; all data will be stored securely in Redcap/secure Box folder. Only those participants who provide consent will complete the additional screening questionnaires. Additional screening measures include additional questionnaires, an expired carbon monoxide sample to confirm smoking status, and (if female) a urine pregnancy test. Participants who are deemed eligible at that point will then complete additional baseline questionnaires. On all correspondence with potential participants, we provide our toll-free number if any questions or problems arise. We will abide by all HIPAA regulations as set forth by our institution. [name] will supervise all aspects of the recruiting process.

### **2.2 Protection Against Risk:**

#### **Use of E-cigarettes**

Participants will be screened for general medical precautions (pregnancy, cardiovascular disease), and all participants will be monitored for adverse events during the study period. We will clearly advise against use of e-cigarettes during pregnancy and breast-feeding and will verify non-pregnancy at study onset. Participants will be educated about potential risks of e-cigarette use, including concurrent use with cigarettes. Any adverse events will be reported to the IRB. The most likely adverse event (potential for nicotine overdose) is anticipated to be rare (~5%) and mild (mouth/throat irritation, headache, nausea, headache), and will be handled quickly (i.e., advice to participant to reduce or stop e-cigarettes). Lab studies of toxin exposure (above) suggest that e-cigarettes confer no greater risk to health than do conventional cigarettes. It is unlikely that e-cigarette users will

become addicted to the product in the 3-week sampling period. All participants will be provided with cessation information (referrals to Quitline) as part of this study. [name] has agreed to serve as the study medical advisor. Both [name] and [name] have worked with [name] in the capacity before, and [name] will be available as needed for consultation on study eligibility criteria or adverse events.

### ***Concurrent Use of E-cigarettes & Smoking***

Per above, the most common effects from too much nicotine are nausea, headache, and disturbed sleep. The sampling period is three weeks in duration, and thus we do not expect sustained patterns of dual use. We will track adverse events at every study contact, and will have a toll-free number available for participants to call if they experience an adverse event (AE). All study contacts will remind participants of this number. Participants will be encouraged to contact study staff as soon as possible for serious events. If they wish, they may contact their local MD or give the study medical advisor permission to do so. We will withdraw participants who have a serious AE, become pregnant or begin breast-feeding. For other AEs, if the study medical advisor ([name]), the participant's physician or the participant wishes it, the participant will be withdrawn from the study.

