Because nicotine delivery and sensorimotor characteristics are a joint function of e-liquid and device characteristics, smokers may choose products that produce the optimal nicotine delivery and sensorimotor stimulation. Thus, we expect (hypothesize) an interaction between concentration and power, and this becomes our **core scientific premise**. A higher-powered device that can deliver greater nicotine per puff of aerosol is likely to be more reinforcing when it is paired with a low nicotine concentration because this combination produces the optimal level of nicotine delivery. Low nicotine concentrations paired with low power may not deliver enough nicotine or provide enough sensorimotor stimulation to be reinforcing, while high nicotine concentrations paired with high power may provide aversive levels of nicotine or an aversive throat hit. Consistent with this prediction, a small study of 20 e-cigarette users found that users of higher powered devices used lower e-liquid nicotine concentrations than users of lower-powered devices, but obtained higher levels of plasma nicotine. Furthermore, a recent survey of 436 current e-cigarette users found a strong negative relationship between the power of device settings and user's chosen e-liquid nicotine concentration ( $r = -0.44$ ). In one experimental lab study, smokers reported that a lower concentration was required to produce the optimal throat hit when using a higher power setting. However, we also know that e-cigarette users can compensate for changes in these characteristics by modifying their puffing behavior. When device power or nicotine concentration are lower, e-cigarette users have been shown to take longer puffs, more puffs, and ultimately consume more e-liquid. Thus, an alternative hypothesis is that these characteristics may be relatively unimportant, as long as users are able to modify their behavior in order to achieve the desired effect. The interactive effects of concentration and power remain unclear, and serve as the central focus of this application.

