### C8. Statistical Considerations:

Power analysis was completed for the primary outcome of percentage reduction in average cigarettes per day smoked in the last week of sampling, and based on data from [name] previous e-cigarette sampling trial during which participants received a low power (1st Gen) device with one of two nicotine concentrations (low or high). We hypothesize that the impact of nicotine concentration on CPD reduction would be similar here for the low power groups and that the effect would be reversed, but of similar size, in the high-power groups (Figure 3a). The hypothesized interaction is shown during the last week of sampling for simplicity in Figure 3b, specifically that for the low power setting, a higher concentration will produce a larger decrease in cigarettes per day than the low concentration, but for the high-power setting, a higher concentration will produce a smaller decrease in cigarettes per day than the low concentration. We use the methods described by Fleiss for estimating power for interaction effects. As he notes, the variance of an interaction effect is four times that of the corresponding main effect. Thus, even large effects require large sample sizes to yield adequate power. In this case, a sample size of 40 participants / group will provide 80% power to detect an interaction among the two factors with a 0.050 significance level, assuming that the common standard deviation is 38% reduction in CPD, as was the case in [name] trial. However, we inflate this sample size by 10%, accounting for attrition over time, and thus aim to **recruit 45 participants randomized per group (total N=180)**.

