## Statistical Analysis Plan

Power analysis was completed for the primary outcome of percentage reduction in average cigarettes per day smoked in the last week of sampling, and based on data from [name] previous e-cigarette sampling trial during which participants received a low power (1st Gen) device with one of two nicotine concentrations (low or high) (84). We hypothesize that the impact of nicotine concentration on CPD reduction would be similar here for the low power groups and that the effect would reversed, but of similar size, in the high-power groups. In this case, a sample size of 40 participants / group will provide 80% power to detect an interaction among the two factors with a 0.050 significance level, assuming that the common standard deviation is 38% reduction in CPD, as was the case in [name] trial (84). However, we inflate this sample size by 10%, accounting for attrition over time, and thus aim to **recruit 45 participants randomized per group (total N=180)**.

For aims 1 and 2, we will assess the impact of concentration and power on each outcome across time using a generalized estimating equation that includes concentration, power, sampling week (time), and their interactions. Hypothesis 1 will focus on percentage reduction in CPD, Hypothesis 2 will focus on e-cigarette uptake (puffs per day), and Hypothesis 3 will focus on complementary measures of preference/demand, all of which are captured at Visit 4. Outcomes that are skewed (e.g., demand parameters, urinary cotinine) will be log transformed. It is possible that reductions in CPD will be bimodal in the last week of sampling, reflecting a subset of participants who may quit smoking during the trial. In this case, we would conduct a Chi-square test on the proportion of participants who reduce their smoking by at least 50%. Exploratory analyses on age will be conducted by adding age to the model. As described in the Career Development Plan, [name] (co-mentor) will be meeting with [name] monthly for training in these analyses, and will also be available to assist with any unexpected issues. Gender will be examined separately as a direct or moderating influence on all outcomes.

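### The adverse-event rule ends study participation with no outcome follow-up described, and the analysis does not say how the resulting missing data are handled across the four cells

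*Combined protocol and SAP*

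**What the plan says.** Protocol section 2.2, under Concurrent Use of E-cigarettes & Smoking, has two routes out.

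- **Mandatory:** "We will withdraw participants who have a serious AE, become pregnant or begin breast-feeding".
- **Conditional:** for other adverse events, "the participant will be withdrawn from the study", but only if the medical advisor, the participant's own physician or the participant wants this.

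Both end participation in the study. Nothing is said about diaries, carbon monoxide (CO) or visits afterwards.

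Other parts of the protocol treat product use and study participation as separate matters. C1 and C5a leave the amount of vaping, including none, to the participant. Section 2.2, under Use of E-cigarettes, expects the likeliest adverse event in about 5% of people, mild, and answered with advice to cut down or stop vaping.

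On where adverse effects might concentrate, A2 says that "high nicotine concentrations paired with high power may provide aversive levels of nicotine or an aversive throat hit".

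The primary outcome in C8 is "percentage reduction in average cigarettes per day smoked in the last week of sampling". C8 and the SAP analyse outcomes "using a generalized estimating equation that includes concentration, power, sampling week (time), and their interactions". Neither states a working correlation, analysis population, missing-data assumption or sensitivity analysis. The only allowance for loss is in the sample size: 40 per group raised to 45 for 10% attrition (C8, SAP), and 200 recruited to obtain 180 (C3).

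**The concern.** The main hypothesis is a concentration-by-power interaction, so each of the four cells carries equal weight in the contrast. If people leave one cell because they react badly to its product, and their smoking would have changed differently from that of those who stay, the observed last-week mean in that cell is biased. The whole bias passes into the interaction.

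The direction cannot be known in advance. If those who leave the high/high cell would have cut down less, the completers overstate that cell's reduction and the hypothesised interaction shrinks. If they would have cut down more, it is exaggerated.

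Extra recruitment replaces numbers but does not correct this. Diary, CO and timeline-followback data not collected after exit cannot be recovered later, although much of it could be obtained at little cost.

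**Working it through.** **Inputs from the documents.** Power: "a sample size of 40 participants / group will provide 80% power to detect an interaction among the two factors", "with a 0.050 significance level" (sidedness not stated; two-sided assumed). Variability: "the common standard deviation is 38% reduction in CPD", so SD = 38 points. Randomised: 45 per cell. (Section 1.1 says 15 per group. That conflicts with 45 and needs reconciling; 45 is used here.)

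**The plan's own figure.** 40/(1 − 0.10) = 44.4, rounded up to 45. Likewise 180/0.90 = 200. Both reproduce.

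**The contrast behind 80% power.** The text gives no numerical effect, so it is back-solved.
- SE of the interaction = 38 × √(4/40) = 12.02.
- Contrast = (1.960 + 0.842) × 12.02 = 33.7 points, or about 16.8 points of concentration effect at each power level.

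**What the inflation protects.** Losing 20 people evenly leaves 40 per cell and 80% power. Losing all 20 from the high/high cell (45/45/45/25) still leaves 77.4%. Precision is therefore not the problem.

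**Bias (assumed inputs).** Suppose each cell loses 5 people for unrelated reasons, and high/high loses a further share of its 45 through adverse-event withdrawal. Suppose the analysis compares observed last-week means, as a GEE with an independence working correlation does. Let D be the assumed difference in percentage reduction between retained and withdrawn participants.

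Bias = p × D, where p = (extra people withdrawn)/40.
Power = Φ((33.7 − bias)/SE − 1.96), with SE = 38 × √(3/40 + 1/n) and n the number left in high/high.

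| Extra high/high loss | People | p | Bias at D = 10 / 19 / 38 | Power, precision loss only | Power if bias attenuates, D = 10 / 19 / 38 |
|---|---|---|---|---|---|
| 5% | 2.25 | 0.056 | 0.6 / 1.1 / 2.1 | 79.4% | 78.1 / 76.8 / 74.0% |
| 10% | 4.5 | 0.1125 | 1.1 / 2.1 / 4.3 | 78.8% | 76.0 / 73.3 / 67.3% |
| 20% | 9 | 0.225 | 2.25 / 4.3 / 8.6 | 77.2% | 71.4 / 65.6 / 52.3% |

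Worked cell: at 10% and D = 38, 4.5/40 × 38 = 4.3 points, which is 12.7% of 33.7. With a true contrast of zero, the type I error is 5.0% to 6.4% over the first two rows and reaches 10.6% only in the most extreme cell.

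**Placing the rows against the protocol.** At about 5%, 0.05 × 180 = 9 such events are expected in the whole trial. The last row needs all 9 to fall in high/high and all to end in withdrawal. The first two rows are the plausible range.

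**Simulation check.** Assumptions: 4,000 replicates, 45 per cell, SD 38, within-person correlation 0.7, true contrast 33.7 in size, about 5% dropout in three cells, and high/high dropout dependent on the previous week's reduction. With 10% high/high dropout and poor responders leaving, the observed-means contrast was 31.0 with rejection 0.76. Maximum likelihood rejected at 0.83. Across all scenarios run, maximum likelihood estimates stayed between 33.5 and 33.9.

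**The case against.** Most of the case against stands.

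- A reader might infer that anyone with an adverse event is removed. The text does not say so. Only serious events, pregnancy and breast-feeding force withdrawal, and the Potential Risks section reports no serious events in the team's current e-cigarette studies.
- Someone who merely dislikes the high/high product can stop vaping and keep contributing data. C1, C5a and the Use of E-cigarettes paragraph all point that way.
- A reader might also infer that data will be lost most in high/high. A2 says only that the combination may be aversive, no cell-specific rate is given, and A2 also allows that users may compensate through their puffing.
- Shifts of 4 to 12 points can be produced by simulation, but they require 18% to 38% dropout in high/high, about 8 to 17 of 45, and an independence working correlation the plan never names. An exchangeable GEE, equally compatible with the plan, recovered the true value in those simulations.

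Three things survive. Exit at the wish of the participant or a physician is still plausibly related to response. The 5% is not a firm ceiling: the risk section cites a crossover study with 38% mouth/throat irritation and 29% nausea at its highest dosage, though these are events rather than withdrawals, and another cited trial found no difference between dose groups. And a plan compatible with both a sound and an unsound analysis has not chosen between them.

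**Conclusion.** The point holds in a limited form. The withdrawal wording ends outcome collection, it does not fit the passages that let a participant stop the product and stay, and the analysis states no approach to the missing data that result. The 10% inflation addresses precision and not validity.

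The likely size is modest: 0.6 to 4.3 points, or about 2% to 13% of a 33.7-point contrast, for 5% to 10% excess loss in high/high. This rests on an assumed 10 to 38 point difference between withdrawn and retained participants, a comparison of observed last-week means, and a contrast back-solved from the stated power. It would approach 8.6 points only if every expected adverse event fell in one cell and led to withdrawal. The documents do not show that the primary result will be seriously biased. They show an avoidable loss of data and an analysis choice left open.

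**What to change.** Leave the clinical stopping rules as they are and reconcile section 2.2 with C1 and C5a by separating stopping the product from leaving the study.

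- **Follow-up.** Participants who stop the product and still consent continue the remote diaries (C5b), timeline followback and CO (C7c), and the non-product assessments at the remaining visits. They are exempt from the Visit 4 product sampling and preference task. The remote questionnaire procedures in C5e can carry part of this.
- **Analysis.** State in the SAP that participants are analysed as randomised. Use all observed weeks in a method valid when dropout depends on observed earlier outcomes: a likelihood-based repeated-measures model, multiple imputation or weighted GEE. If a GEE is kept, name its working correlation.
- **Reporting.** Tabulate withdrawals by cell and reason, with a sensitivity analysis that lets unobserved outcomes differ by cell.

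The cost is a short protocol edit, a paragraph in the SAP, a few extra diary and visit payments, and slightly more analysis. Participants who withdraw consent will still be lost, so the sensitivity analysis is needed in any case.
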